Traditionally, group-based CBT (GCBT) for PTSD has involved ET, CT, and relapse prevention training components (e.g., Foy et al., 2000; Shea et al., 2009). Group sizes have ranged from 2 to 8 members and treatment duration has ranged from 6 to 30 sessions. As summarized by Shea et al. (2009) and [name], Bovin, and Schnurr (in press), studies have examined GCBT with trauma populations including adult women who experienced childhood sexual abuse, combat veterans, female survivors of sexual or multiple other traumas, and dyads involving mothers and their sexually-abused children. Although not as developed as the individual CBT literature, these studies indicate that GCBT on average has a 0.68 effect size (Hedges' unbiased estimator, range .24 to 1.09). Unfortunately, this literature has methodological limitations, including lack of randomization to treatment/control conditions, an absence of control groups, treatments that were not manualized, and lack of monitoring of therapist adherence and competence. While recognizing these concerns as well as the apparent diversity among available interventions (with respect to group size, length, and content), Foy et al. (2000) drew three conclusions: 1) group therapy shows efficacy for PTSD, although the number of studies involving male patients is limited, 2) methodological limitations reduce the strength of conclusions that can be made about GCBT in general (an opinion shared by Shea et al., 2009 and [name], Bovin, and Schnurr, in press), and 3) Foy et al. and Shea et al. highlight the importance of expanding research on group therapy into applied settings, to merge efficacy and effectiveness research in an effort to increase the utility of group treatment. Some of these issues can be addressed via a well-controlled RCT, involving manualized treatment, an appropriate comparison condition, use of experienced therapists, inclusion of therapist adherence and competency checks, and the use of independent assessors, features that are included in this proposal.

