In keeping with the recommendations of Foy and colleagues, Schnurr et al. (2003) examined the impact of Trauma-focused Group Therapy (TFGT) with 360 Vietnam veterans within the VA system (VA Cooperative 420 Study). TFGT involved groups of 6 male patients who met weekly for 30 weeks, followed by 5 booster sessions. Importantly, TFGT began ET slowly, waiting to introduce the technique until session 12. ET was conducted and shared within the group format (each group member listened to each others' exposure items). TFGT was compared with a Present-Centered Group Treatment (PCGT) that focused on current problems and avoided a trauma focus. Results indicated that patients in both treatment conditions showed improvements (average of 40% showing clinically significant change), although no difference was noted between the two interventions. Narrowing the analyses to veterans who had received

an adequate dose of treatment (at least 24 sessions) indicated that TFGT was marginally more efficacious in reducing avoidance and numbing symptoms and possibly overall PTSD symptom severity ( $p = .06$ ). Schnurr et al. (2003) discuss the role of in-session exposure in these outcomes, indicating that perhaps the “dosage” of ET was not sufficient in TFGT. In considering TFGT, it is notable that this treatment program is fairly long (30 sessions) and requires some degree of distress tolerance from veterans, given that ET was conducted within the group. Recently, Ready et al. (2008) presented data from an uncontrolled trial of Group Exposure Therapy, which is somewhat similar to TFGT; the pre-to-post effect size was 1.20 in a sample of veterans with combat-related PTSD. Although promising, these studies suggest that group-based treatments for PTSD warrant continued study.

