C. 2. Preliminary Studies: This investigative team has experience with research focusing on psycho-pathology, assessment, and treatment of PTSD. The work that is particularly germane to this application stems from a development grant from NIMH (R21 MH64777, PI [name]) that provided preliminary support for a GCBT to treat	CAPS Avoid/ Numbing	22.8 (6.7)	11.1 (8.6)	7.2 (7.6)	21.9 (7.5)	20.9 (12.6)	.89
	CAPS Phy. Hyper.	17.4 (6.5)	9.5 (7.9)	7.3 (7.7)	16.9 (5.7)	13.1 (8.0)	.43
	# patients PTSD +	17/17 (100%)	2/17 (11.7%)	1/15 (6.7%)	16/16 (100%)	11/16 (68.7%)	
	IES-R Intrusion	1.8 (0.8)	0.9 (0.9)	0.7 (0.7)	2.2 (0.9)	1.9 (1.2)	1.04
	IES-R Avoidance	1.5 (0.8)	0.7 (0.8)	0.6 (0.8)	1.8 (0.9)	1.5 (1.0)	.83
	IES-R Phy.	1.8 (0.9)	1.3 (1.2)	0.9 (0.8)	2.5 (1.0)	2.3 (1.1)	.83
	Hyper.						

PTSD. The initial part of this grant developed the GCBT protocol, including writing the manual devising instruments to assess therapist adherence and competence, and testing the treatment with several groups of patients ([name] & Coffey, 2005). The second part of this grant included the conduct of a small RCT ([name], Coffey, Foy, Keane, & Blanchard, 2008). Individuals ( $N = 45$ ) with chronic PTSD related to a serious MVA were randomly assigned to either GCBT or a minimum contact comparison group (MCC) in which patients were repeatedly contacted by phone, to assess current functioning and symptomatology.

As reported in **Table 1**, compared with the MCC participants, individuals who received GCBT showed significant reductions in PTSD symptoms, whether assessed using clinical interview (using assessors who were unaware of treatment status & assessment point) or self-report measures. Following treatment, 88.3% of GCBT participants did not satisfy criteria for PTSD, relative to 31.3% of the MCC participants. Examination of anxiety and depression measures did not show a unique advantage of GCBT, although reduced power from the small sample size is relevant here. Treatment-related gains were maintained over a 3-month follow-up interval. Patients reported satisfaction with GCBT and attrition from this treatment was comparable with other individual-format CBT's (see also [name] et al., 2009).

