**Is this RCT adequately statistically powered?** In the study design, several factors were involved in determination of sample size. **First**, we drew estimated effect sizes from the **two** pilot studies on GCBT and from a recent meta-analysis (Bradley et al., 2005). Within the MVA pilot study, which contrasted GCBT with a minimal contact comparison condition, effect sizes for PTSD measures ranged from .83 to 1.04 (Hedges's unbiased  $g$ , Hedges, 1981). Within our Vietnam veteran pilot data, the pre-post treatment effect size for the PCL-M was  $d = 1.43$ . Consulting the larger literature, Bradley et al. (2005) computed average effect sizes (Cohen's  $d$ ) of .84 for contrasts between CBT versus supportive therapy conditions and 1.01 for contrasts between ET + cognitive therapy versus supportive therapy conditions. However, in RCTs involving veterans, effect sizes tend to be smaller, owing to the chronicity and severity of combat-related PTSD in this population. In computation of sample size for this trial, we have selected a relatively low value of  $d$  (.50); review of available studies (including our own pilot data) suggests effect sizes ranging from 0.84 to 1.43. Recognizing that effect sizes for contrasts between CBT and supportive psychotherapy tend to average  $d = .84$  (Bradley et al., 2005), that data from samples with chronic PTSD tend to have smaller effects, relative to less severe samples, and that effect sizes drawn from relatively small samples can be unstable, we took a conservative stance in estimating the effect size for the GCBT versus SGP contrast to arrive at  $d = .50$ . **Second**, because treatment within both conditions of this RCT will occur in groups, the analytic plan must account for the cluster effect owing to the correlation of outcomes within groups (expressed as  $\rho$ , the intraclass correlation coefficient). There is one clustered variable in this design (individuals within groups) which will be adjusted for in determining sample size. Following guidelines provided by Hsieh (1988) and Diggle et al. (2002), we used an inflation factor that was driven by the  $\rho$  values from the MVA-related PTSD pilot data. In particular, the  $\rho$  estimate of 0.11 is a conservative assumption, based on the largest value obtained in the pilot MVA study. In the pilot MVA study ([name] et al., 2009), the  $\rho$  for the CAPS was 0.07, the  $\rho$  for the BDI-II was 0.03, and for the BAI, the  $\rho$  was 0.08. Within the Collaborative 420 study (Schnurr

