
et al., 2003), the  $\rho$  for the CAPS was 0.05. Thus, use of  $\rho = 0.11$  in our power calculations is a conservative assumption. Larger values of the  $\rho$  can occur when the outcome measures (among patients) have a concrete connection to one another. In studies of physician behavior within a clinic, the  $\rho$  values are larger when the physician directly contributes to the assessment of the patient outcome measures. For example, Stedman et al. (2008) analyzed two such studies, one study of patients within selected clinics who were followed to determine if their clinic physician did or did not provide osteoporosis management, and a second study of patients within clinics to determine if physician education induced physicians to improve the quality of osteoporosis management. In each study the  $\rho = 0.12$ . The outcome measure for the patient was the level of disease management delivered by the physician, an outcome directly determined by the physician. In contrast, for our proposed study, the person who assesses patient outcomes should have little or no effect on the values of the patient measure outcome. In our study, the  $\rho$  captures a subtler effect, namely, potential assessor bias, a much smaller effect than the effect of physician practice patterns. With a proposed group size of 7, a maximum  $\rho$  of 0.11, and  $d = 0.50$ , we estimated a total  $n$  of 196, using  $p < .05$ . Although only two of 14 outcome variables in the pilot study exceeded  $\rho > .10$  (see [name] et al., 2009), we felt it was preferable to be conservative regarding  $\rho$  levels in our power computations. **Third**, in computation of sample size, we relied on .80 power level, as is customary in power calculations for RCTs. Using these parameters, the total desired  $n$  will be 196 ( $n = 98$  per condition); each treatment group will begin with 7 men. Thus, based on previous studies on Group CBT, as well as current data regarding ICC in the context of clinical trials, we have been appropriately conservative in our power calculations.

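### The power section misreports the effect sizes behind d = .50, so the claim that .50 is conservative is not demonstrated, and power at the plan's own .30 threshold is about 37%

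*Combined protocol and SAP*

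**What the plan says.** The paragraph asking whether the trial is adequately powered (section D, after D.6) names its sources as two pilots and one meta-analysis. It makes four statements about effect size:

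- In the accident pilot, against a minimal-contact comparison, "effect sizes for PTSD measures ranged from .83 to 1.04".
- In the veteran pilot, the pre-post effect on the PCL-M was d = 1.43. The meta-analysis gave .84 for CBT against supportive therapy.
- In summary, "review of available studies (including our own pilot data) suggests effect sizes ranging from 0.84 to 1.43".
- For the sample size, "we have selected a relatively low value of" d, namely .50. The reasons given are veterans' chronicity and the instability of small-sample estimates.

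It closes that "we have been appropriately conservative in our power calculations", and rests this on earlier work on group CBT and on ICC data.

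Other parts of the document bear on the same question:

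- C.2, Table 1 (the same accident pilot): "CAPS Phy. Hyper. 17.4 (6.5) 9.5 (7.9) 7.3 (7.7) 16.9 (5.7) 13.1 (8.0) .43".
- B.2, on the group-CBT literature: "these studies indicate that GCBT on average has a 0.68 effect size", with a range of .24 to 1.09.
- B.2, on a 360-man Vietnam veteran trial of trauma-focused against present-centered group treatment: "no difference was noted between the two interventions".
- D.6 labels this trial's own SGP comparator as present-centered group treatment.

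The next paragraph, on clinical significance, cites d of .30 or more as meaningful between two active treatments. It then concludes that the planned number is enough to determine whether outcomes are clinically meaningful.

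**The concern.** The two ranges are what make .50 look low: if every relevant effect were at least .83, .50 would be a deep discount. The document's own figures do not support those ranges. The omitted items include the evidence closest to this trial in format (group CBT) and the one trial that also shares its population and type of comparator. The power section does use that veteran trial, but only for its ICC of .05 and not for its treatment result.

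What is at stake is how a null result would be read. Someone who accepts that the calculation was conservative, and that the sample was sufficient for clinically meaningful effects, would take a null finding as evidence against any useful difference. At the threshold the plan cites, the trial would more likely miss a true effect than find it.

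**Working it through.** **1. Is the .43 real?** Table 1 gives post-treatment CAPS hyperarousal of 9.5 (SD 7.9), n = 17, against 13.1 (SD 8.0), n = 16.

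- Pooled SD = √[(16 × 7.9² + 15 × 8.0²)/31] = 7.95
- d = 3.6/7.95 = .453
- Small-sample correction 1 − 3/(4 × 31 − 1) = .976, so g = .44

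This agrees with the printed .43. The avoidance/numbing row, treated the same way, gives .89 as printed. So .43 is a between-group post-treatment effect on a PTSD measure, and it lies outside .83 to 1.04.

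**2. The 0.84 to 1.43 range.** It is said to include the pilot data, but it excludes .43 and also the .83 quoted a few sentences earlier. Its top is labelled pre-post, so it is not a GCBT-versus-control contrast. For the same PCL-M change, C.2 also prints 1.36 (Table 2) and 1.35 (text).

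**3. Where .50 sits.** It is below .68 and .84. It is above .43 and above .24, the bottom of the group-CBT range. The veteran trial is reported without an effect size.

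**4. The plan's sample size.** Inputs: d = .50, ICC .11, groups of 7, power .80, p < .05. Sidedness is not stated; two-sided is assumed.

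- Unclustered n per arm = 2 × [(1.960 + 0.842)/.50]² = 62.8
- Design effect = 1 + 6 × .11 = 1.66
- 62.8 × 1.66 = 104.2, so 105 per arm, 210 in total

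The stated 196 is not reproduced. A one-sided test gives 166. With full groups of 7, 196 fits an ICC of about .08 to .09.

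**5. Power with 98 per arm.** Normal approximation, two-sided: power = Φ(d/SE − 1.96), with SE = √(2 × design effect/98). SE is .184 at ICC .11 and .170 at ICC .07, the pilot's CAPS value (design effect 1.42).

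| d | ICC .11 | ICC .07 |
|---|---|---|
| .24 | 26% | 29% |
| .30 | 37% | 42% |
| .40 | 58% | 65% |
| .43 | 65% | 71% |
| .50 | 77.5% | 84% |
| .68 | 96% | 98% |

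Example, d = .30 at ICC .11: .30/.184 − 1.96 = −.33, and Φ(−.33) = 37%. For d = .40: .40/.184 − 1.96 = .21, and Φ(.21) = 58%.

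**6. Sensitivity at ICC .11.** A t-test on 26 cluster-level degrees of freedom gives 34.8% at .30 and 74.4% at .50. A one-sided test gives 49.4% and 85.8%. The smallest d detectable with 80% power (two-sided, normal) is 2.80 × .184 = .516.

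**The case against.** The strongest reply is that a planning value is conservative when it lies below the expected effect, not below every estimate. On that view .50 passes: it is below the .68 group-CBT average, where power is about 96%, and below the .84 for CBT against supportive therapy. The section also marks d down openly for veterans, chronicity and small samples. This stands, and it rules out several stronger readings a reader might infer.

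- **That .50 is shown not to be conservative.** Including .68 helps the plan, and .43 is one CAPS subscale, whereas Hypothesis 1 is tested on the CAPS total. The pilot's CAPS-total effect is not in the part of Table 1 available here.
- **That the pilot range is exactly .43 to 1.04.** The visible rows show only that it goes down at least to .43.
- **That the veteran trial means d = 0.** B.2 reports no difference and gives no effect size. It describes a longer treatment (30 weekly sessions plus boosters, with exposure introduced at session 12 and shared in the group) and p = .06 for a possible benefit on overall severity among adequately treated men.
- **That .24 to 1.09 are between-group effects.** B.2 does not say so, and lists missing control groups among that literature's weaknesses.
- **That 1.43 is miscalculated.** Dividing the change by the pooled pre/post SD gives 14.0/11.4 = 1.22, but the value depends on the standardiser, and the plan does label it pre-post.

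The .68 and the veteran trial were left out, not misquoted. The reply does not rescue the two printed ranges or the claim of sufficiency at .30.

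**Conclusion.** The concern holds in limited form. Both printed ranges conflict with the document's own figures, one of them is topped by an uncontrolled change, and two directly relevant items of evidence are left out. The result is that .50 lies within the plan's evidence, with two averages above it and some values below it. Its conservativeness is undemonstrated; the documents do not disprove it.

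The practical size lies in what 196 men can detect: about 37% power at d = .30 and 77.5% at .50 with the plan's ICC of .11, or 42% and 84% with ICC .07. The statement that the sample suffices for clinically meaningful effects does not follow from the .30 threshold cited just before it; even a one-sided test gives under 50% there.

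These figures assume a two-sided 5% test (sidedness is not stated), full groups of 7, a simple comparison of means with a design effect, and no missing data. The plan gives no repeated-measures correlations, so any gain from the growth model cannot be credited.

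**What to change.** Amend the text only. The sample size and the analysis stay as they are.

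1. State that the visible pilot effects on PTSD measures go down to .43, and give the pilot's CAPS-total effect if it is available.
2. Add the group-CBT average of .68 (.24 to 1.09), after checking whether those are between-group or pre-post effects. Cite the veteran trial as no difference reported, not as d = 0.
3. List pre-post values separately from between-group values, and reconcile 1.43, 1.36 and 1.35 for the PCL-M.
4. Justify the word conservative for d = .50 against this fuller list, or drop it.
5. State the sidedness, and print power for 196 men at ICC .11: about 37% at d = .30, 58% at .40 and 77.5% at .50 (42%, 65% and 84% at ICC .07).
6. Reword the clinical-significance paragraph so that it no longer says the sample suffices for clinically meaningful effects while citing .30 as the threshold.

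The cost is a few sentences and a less favourable stated justification. No additional participants are proposed.

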Although the results of this pilot study are promising, there are several limitations that need to be addressed in the design of a larger RCT, as proposed here. Among these limitations is the fact that the sample size was small and so, analyses could not account for the natural clustering of patients within treatment groups in the GCBT arm. The statistical power also is lower than desired, given the sample size. Even in the face of these limitations, these pilot data suggest that GCBT may be an effective format for the treatment of PTSD and support the current application.

Importantly, we (Drs. [name], [name] and [name]) modified the GCBT manual to be appropriate to the treatment of PTSD in Veterans and collected pilot data from two treatment groups. We retained the basic format of the GCBT (14 sessions, 2 hours per session, 2 therapists) and the

content was largely unchanged. The exposure-based components of GCBT were modified based on input from these groups; specifically, we increased emphasis on in-vivo exposure and modified imaginal exposure to focus on events that occurred in combat, using narrative writing to guide exposure.

Thus, exposure homework focuses on in-vivo experiences with current trauma cues and trauma writing about specific events relating to combat. Because the exposure components of treatment are conducted as homework assignments that take place outside of group sessions, the men who participated in the two pilot groups reported that this type of exposure was much more tolerable than prolonged exposure. The group environment was frequently mentioned as important in providing motivation for exposure, given the built-in social support. Additionally, we modified some of the cognitive intervention components to recognize affect other than anxiety.

Importantly, we modified all patient handouts, therapist outlines, and template sessions notes, in order to test this GCBT with veterans. These modifications represent “fine-tuning” more than extensive modification of the GCBT, as it was initially developed. As such, we are confident that any remaining modifications similarly will be relatively minor and straight-forward, particularly given our experience with two pilot groups.

Two pilot groups have been run using the revised manual for use with veterans (one group each at VA Boston and VA Providence).

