extent of dependency (i.e., clustering) by calculation of intraclass correlations (ICCs) using variance estimates from unconditional cell means models of key outcome variables (cluster = treatment group). Our proposed  $N$  of 196 will be clustered into 14 treatment groups per condition. Assuming non-zero ICCs, a multilevel approach will be incorporated into the latent growth framework in order to obtain correct standard errors, test statistics, and confidence intervals. In the traditional multilevel modeling, the design would be construed as a three-level model; i.e., repeated observations (Level 1) nested under individuals (Level 2), individuals nested under treatment groups (Level 3). However, because the first two levels are combined in the multivariate framework of latent growth modeling, this design can be characterized as a two-level model (i.e., latent growth factors are nested under treatment groups) where time-invariant covariates (i.e., dummy codes for treatment condition) are included to account for the within-group and between-group variability in initial status (pre-treatment) and symptom change (improvement over active treatment and follow-up). In the latent growth model portion of the models, the intercept will be centered on pre-treatment (i.e., first slope loading will be fixed to 0.0). Because there is no substantive interest in the form of the growth trajectory, intermittent time points (i.e., slope factor loadings) will be freely estimated and the final timepoint of interest (e.g., post-treatment) will have a corresponding factor loading fixed to 1.0. Accordingly, the mean and variance of the slope will convey the fixed (average) and random effects (individual differences) of change for the given time interval of interest. The Level 2 variables of treatment condition (single dummy code using *SGP* as reference group) will be included as predictors to account for individual differences in treatment response and variability in outcome across treatment groups. To examine pre-treatment differences between treatment conditions, the intercept (centered on pre-treatment) will be regressed onto the treatment covariates (i.e., significant paths are indicative of differences in pre-treatment levels as a function of treatment condition). Any pre-treatment differences will be accommodated into the interpretation of findings and in the parameterization of the models (e.g., regression of the slope onto the intercept, as well as covariates such as treatment condition). The dependent variable for this analysis is the CAPS total score. Additionally, PCL will be examined, using the same analytic approach, in order to examine respondent effects (interviewer-rated versus self-report).

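### The power section explains rho as assessor bias and calls .11 a maximum, and at that rho n = 196 gives about 77.5% power, not 80%

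*Combined protocol and SAP*

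**What the plan says.** In the combined protocol and SAP, the section *Is this RCT adequately statistically powered?* says that, because both arms are treated in groups, "the analytic plan must account for the cluster effect owing to the correlation of outcomes within groups". It names one clustering variable, individuals within groups. Section D.7.a agrees: ICCs are to be estimated with the treatment group as the cluster, and the sample "of 196 will be clustered into 14 treatment groups per condition".

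The planning value is rho = .11, introduced as the biggest value seen in the motor-vehicle-accident pilot. The section also reports a CAPS rho of .07 from that pilot and .05 from the earlier VA cooperative trial of group therapy. It adds that only two of 14 pilot outcomes were above .10. It then compares the trial with two studies of physician behaviour (rho = .12) and argues that rho here should be smaller because it "captures a subtler effect, namely, potential assessor bias, a much smaller effect than the effect of physician practice patterns". In the sample-size sentence, .11 is described as a maximum.

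The remaining inputs are d = .50, p < .05 with no sidedness given, and groups of seven ("each treatment group will begin with 7 men"). On power, "we relied on .80 power level, as is customary in power calculations for RCTs". The result is a total of 196, or 98 per arm, and the section closes by calling its power calculations conservative.

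**The concern.** Two things look wrong in the reasoning, and one in the arithmetic.

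First, assessor bias is not the quantity that inflates the variance here. The design effect comes from similarity among seven men treated together. Keeping assessors blind and separate from treatment does not reduce that similarity. So the contrast with the physician studies gives no reason to expect a small treatment-group rho.

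Second, the largest of several point estimates is not an upper bound. The section gives no interval and no number of pilot groups. Section C.2 says of the same pilot that, because the sample was small, "analyses could not account for the natural clustering of patients within treatment groups in the GCBT arm".

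Third, the design effect determines the sample size, so the stated .80 should be recoverable from the stated inputs. If it is not, readers are relying on a power figure that the design does not deliver.

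**Working it through.** **Inputs from the documents.** d = .50; rho = .11; group size m = 7; power .80; alpha .05; 98 per arm; 14 groups per arm. Assumed: two-sided test, equal groups, all 196 contributing data.

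**Step 1: reproduce the plan's n.**
- Per arm without clustering: 2 × ((1.960 + 0.842)/0.50)² = 62.8, rounded up to 63.
- Design effect: 1 + (m − 1) × rho = 1 + 6 × .11 = 1.66.
- Per arm with clustering: 63 × 1.66 = 104.6, rounded up to 105. Total 210, not 196.
- One-sided .05: 50 × 1.66 = 83 per arm, total 166. This does not give 196 either.
- Two-sided .05 gives 196 if one input is changed. With groups of 6 and rho .11, 63 × 1.55 = 97.65, rounded up to 98 per arm. With groups of 7 and rho .09, 63 × 1.54 = 97.02, rounded up to 98 per arm. The section states neither combination.

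**Step 2: power at n = 196 with the stated inputs.**
- SE(d) = √(2 × 1.66/98) = 0.184.
- d/SE = 0.50/0.184 = 2.716.
- Normal approximation: Φ(2.716 − 1.960) = Φ(0.756) = 77.5%.
- Noncentral t with 2 × (14 − 1) = 26 df: 74.4%.
- One-sided, for comparison: 85.8% (84.1% on 26 df).

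**Step 3: the largest rho at which .80 holds.** (98/62.79 − 1)/6 = .093 (two-sided, normal approximation), which is below the plan's own .11.

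**Step 4: power of the fixed n = 196 over a range of rho** (d = .50, m = 7, two-sided .05).

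| rho | Design effect | Normal | t, 26 df |
|---|---|---|---|
| .05 (CAPS, VA cooperative trial) | 1.30 | .87 | .84 |
| .07 (CAPS, pilot) | 1.42 | .84 | .81 |
| .11 (plan) | 1.66 | .78 | .74 |
| .15 | 1.90 | .72 | .69 |
| .20 (pessimistic) | 2.20 | .66 | .62 |

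**Step 5: can rho above .11 be ruled out?** Section B.2 puts the VA cooperative trial at 360 veterans in groups of 6. The number of groups behind its rho of .05 is not given. The one-way ANOVA interval uses F = (1 + (m − 1)r)/(1 − r) = 1.25/0.95 = 1.32. If there were 60 groups (360/6), the 95% interval is about −.02 to .14. If only 30 groups were used, it is about −.04 to .20. Values somewhat above .11 are therefore not excluded, and .20 is at or beyond the edge.

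**The case against.** The strongest defence is that .11 is a sensible choice whatever one thinks of the sentence offered in support. It exceeds both cited CAPS values, one of them from a much larger trial in veterans treated in groups. At those values n = 196 does reach .80 (.84/.81 at .07 and .87/.84 at .05). The section also concedes that larger values can occur, and *maximum* can be read as the largest observed. Moreover, D.7.a estimates the ICCs and fits a multilevel model, so the validity of the primary test does not depend on the planning rho. All of this stands. It does not rescue the assessor-bias argument, and it does not make the stated inputs yield .80.

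A reader might go further and infer that .11 is unsupported, because a pilot with 17 GCBT patients in its outcome table could hide a very large rho. If those 17 were in 3 to 5 groups, the 95% upper limit around .11 would be .77 to .92. The documents do not support relying on that. They give neither the number of pilot groups nor the sample behind the pilot rhos. The outcome that gave .11 is not identified, and it is the largest of several estimates, whereas the pilot CAPS value was .07.

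Sidedness is the other open point. The hypotheses are directional, and a one-sided test would put power above .80. The section does not say that one was planned, and a one-sided calculation does not give 196.

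**Conclusion.** The point holds in three limited respects. The assessor-bias rationale contradicts the plan's own definition of rho. *Maximum* overstates what is a largest pilot point estimate without an interval. And the stated .80 is not delivered at the stated inputs: power is 77.5% (normal) or 74.4% (26 df), a shortfall of about 2.5 to 5.6 percentage points.

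These figures assume a two-sided .05 test, equal groups of seven and no missing data. Missing data would lower them. The baseline and repeated measures in the growth model could raise them, but the plan gives no correlations and its calculation does not use them. The choice of d = .50 is taken as given.

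The documents do not show that .11 is too low for the CAPS, that rho is likely to be near .20, or that the planned analysis is invalid.

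**What to change.** In the power section:

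- Delete the assessor-bias argument and the comparison with the physician studies that leads to it.
- Define rho once, as the treatment-group intraclass correlation, in line with D.7.a.
- Replace *maximum* with *largest pilot estimate*. Limit the claim of caution about rho to the comparison with the cited CAPS values of .07 and .05.
- State whether the test is one- or two-sided.
- Replace the single .80 with the power of the fixed n = 196. If two-sided (normal / 26-df t), this is .87/.84 at rho .05, .84/.81 at .07, .78/.74 at .11 and .72/.69 at .15, with .66/.62 at .20 marked as a pessimistic case.

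The cost is a less favourable statement of power and a few lines of protocol text. Sample size, design and analysis are unchanged, and no extra patients are needed. If a different group size, rho or sidedness was in fact used to reach 196, the section should say so and show the calculation.
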